## **6 Safety and Adverse Events**

Given this study is observational in nature and COVID-19 vaccines are administered as part of standard of care, reactions to COVID-19 vaccines **are not** considered an AE. If a subject has a reaction to a vaccine, investigators are encouraged to report those events to the FDA through MedWatch as they would through normal standards of practice. Patients may also submit any vaccine-related adverse events to the Centers for Disease Control and Prevention's Vaccine Adverse Event Reporting System.

There are no study procedures that are expected to generate adverse events.

## **7 Study Administration, Data Handling, and Record Keeping**

### **7.1 Confidentiality**

Information about study subjects will be kept confidential and managed according to the requirements of the Health Insurance Portability and Accountability Act of 1996 (HIPAA). These regulations require a signed subject authorization informing the subject of the following:

- What protected health information (PHI) will be collected from subjects in this study.
- Who will have access to that information and why.
- Who will use or disclose that information.
- The rights of a research subject to revoke their authorization for use of their PHI.

In the event that a subject revokes authorization to collect or use PHI, the investigator, by regulation, retains the ability to use all information collected prior to the revocation of subject authorization. For subjects that have revoked authorization to collect or use PHI, attempts should be made to obtain permission to collect at least vital status (i.e., that the subject is alive) at the end of their scheduled study period.

### **7.2 Data Collection and Management**

All data will be collected and stored in the Data Hub. Data collection will be done from subjects' existing medical records and/or manual data entry into the Data Hub's electronic data capture form via a website or mobile application.

### 7.3 Physical Security and Access Control

The Data Hub provides end-to-end protection for all data, both in transit and at rest. Data Hub application environments use GPG with AES 256 encryption; all end-user connections to Data Hub Portals are encrypted using SSL; file transfers are conducted over SFTP or HTTPS; and all received FHIR messages and data files are individually encrypted with GPG before archiving in an AES 256 encrypted environment. Data is also archived to the Data Hub's secure cloud backups service. Everything contained on the Data Hub server is encrypted (e.g., GPG, AES256), and all data sent to and from the server is encrypted. All backups are encrypted with GPG before transmission.

### 7.4 Study Monitoring

Study data entered in the Data Hub will be reviewed by the study sponsor or designee on a regular basis to ensure data quality and timely data entry.

## 8 Ethical Considerations

This study is to be conducted in accordance with applicable United States government regulations and international standards of Good Clinical Practice, and applicable institutional research policies and procedures.

This protocol and any amendments will be submitted to a properly constituted independent Ethics Committee (EC) or IRB, in agreement with local legal prescriptions, for formal approval of the study conduct. The decision of the EC/IRB concerning the conduct of the study will be made in writing to the investigator and a copy of this decision will be provided to the study sponsor before commencement of this study.

### 8.1 Vulnerable Populations

Investigators should exercise discretion in ensuring that human subjects that may be vulnerable (prisoners, educationally disadvantaged, economically disadvantaged, or individuals with impaired decision making) undergo appropriate enrollment procedures and are protected.

### 8.2 Risks

**Risk of loss of confidentiality:** There is small risk of loss of confidentiality if identifiable data were inadvertently accessed by someone outside the study team. This risk is minimized by the use of secure storage methods.

### 8.3 Benefits

Subjects are not expected to directly benefit from this study. Knowledge gained from this study may benefit subjects with multiple myeloma.

## 8.4 Risk-Benefit Assessment

The procedures in this protocol are of minimal risk. The benefit and relevance of the knowledge gained from this study offset the risks associated with participating.

## 9 Study Finances

### 9.1 Funding Source

ASH Research Collaborative is the sponsor of the study, with funding support from Moderna Therapeutics.

### 9.2 Subject Payments

Modest remuneration will be provided to participants in the study to help defray the cost of participation. The following represents the projected compensation scheme for each subject; however, payments may be made in installments that accommodate participant scheduling.

Subjects will receive up to a total of \$400 for completing all study visits:

- **Time 0:** \$200 upon completion of enrollment activities (study ICAF, EHR data transmitted, PGHD, and PROs)
- **Time 1:** \$100 (EHR data transmitted, PGHD, and PROs)
- **Time 2:** \$100 (EHR data transmitted, PGHD, and PROs)

## 10 Key Personnel

Key study personnel include:

- Co-investigators
- ASH RC staff
- Subcontractors (as outlined below)

ASH RC will subcontract with the following organizations for the conduct of this study:

### **Breakthrough Healthcare**

Breakthrough Healthcare provides clinical registry services, clinical dataset and measures development, program and service design, and organizational strategy services. Our clients include nonprofit medical societies, healthcare membership associations, government agencies, and data-driven healthcare enterprises.

### **Eureka Research**

The cloud-based healthcare platform designed to empower people with their digital health data. The company's platform offers secure acquisition, harmonization, and utilization of health-related data from electronic health record and billing systems, surveys, wearables, sensors, and medical devices, enabling

users to embrace the potential of their health information and gather all their data into one place to improve health for themselves, their family, and for society.

### **IQVIA**

IQVIA, the Data Hub's technology vendor, brings together advances in data science, technology, and healthcare expertise to help customers make better decisions and ultimately improve patient outcomes.

### **Yale Center for Outcomes Research & Evaluation**

Yale Center for Outcomes Research & Evaluation (Yale CORE) is a leading national outcomes research center working on select projects designed to assess healthcare quality and evaluate clinical decision making and comparative effectiveness of specific healthcare interventions. Yale CORE will leverage its' scientific expertise and infrastructure to provide comprehensive data analytic services for this project.

## Appendix A: Patient-Generated Health Data Elements

### Time 0 (Baseline)

Registration Questions			
First Name		Middle Name	
Last Name		Date of Birth (DOB)	/ /
Email Address Required for payment purposes.		Phone Number (optional)	( ) - - O Decline to Provide

#### Before Informed Consent

Eligibility Survey	
Do you have access to your online medical records (patient health portal) or would you be willing to activate it?	O Yes O No
Have you been diagnosed with multiple myeloma?	O Yes O No
Are you currently receiving treatment for multiple myeloma?	O Yes O No

#### After Informed Consent

Participant Information			
Socio-Demographics			
Birth sex	O Male O Female O Other O Decline to Answer		
What race(s) do you identify as? (Select all that apply)	 American Indian or Alaskan Native  Asian  Black or African American  White  Native Hawaiian or Other Pacific Islander  Other  Decline to Answer		
Hispanic ethnicity	O Hispanic or Latino/Latina O Not Hispanic or Latino/Latina O Decline to Answer		
COVID-19 History			
List all COVID-19 vaccinations received.			
Have you received a COVID-19 Vaccination?	O Yes O No O I Don't Know		
Vaccination date	Which vaccine dose(s) did you receive?		Which vaccine did you receive?
/ (MM/YYYY) O I Don't Know	O First Dose O Second Dose O Booster(s) O I Don't Know		O Pfizer O Moderna O Johnson & Johnson O Novavax O I Don't Know
/ (MM/YYYY) O I Don't Know	O First Dose O Second Dose O Booster(s) O I Don't Know		O Pfizer O Moderna O Johnson & Johnson O Novavax O I Don't Know
/ (MM/YYYY) O I Don't Know	O First Dose O Second Dose O Booster(s) O I Don't Know		O Pfizer O Moderna O Johnson & Johnson O Novavax O I Don't Know
/ (MM/YYYY) O I Don't Know	O First Dose O Second Dose O Booster(s) O I Don't Know		O Pfizer O Moderna O Johnson & Johnson O Novavax O I Don't Know
/ (MM/YYYY) O I Don't Know	O First Dose O Second Dose O Booster(s) O I Don't Know		O Pfizer O Moderna O Johnson & Johnson O Novavax O I Don't Know
If you have not received any COVID-19 booster vaccinations, would you be willing to be contacted to discuss the benefits and risks of obtaining one?			O Yes O No O I Don't Know
Would you be willing to receive a yearly COVID-19 vaccination if recommended by your physician?			O Yes O No O I Don't Know
COVID-19 Infections			
List all current and prior COVID-19 infections.			
Have you been diagnosed with COVID-19?	O Yes O No O I Don't Know		
When was your COVID-19 Infection Confirmed?	/ (MM/YYYY) O I Don't Know	How was your COVID-19 Infection Confirmed?	O Home Test Kit O Diagnosis by a Healthcare Professional O I Don't Know
Did This COVID-19 Infection Cause You to be Hospitalized?	O Yes O No O I Don't Know	If Yes, About How Many Days Were You in the Hospital?	- O I Don't Know

## Time 1 (30 Days) and Time 2 (180 Days)

COVID-19 History			
List all COVID-19 vaccinations received since you completed the Baseline questionnaire.			
Have you received a COVID-19 vaccine since your last visit?		 Yes  No  I Don't Know	
Vaccination Date	Which Vaccine Dose Did You Receive?	Which Vaccine Did You Receive?	
/ (MM/YYYY)  I Don't Know	 First Dose  Second Dose  Booster(s)  I Don't Know	 Pfizer  Moderna  Johnson & Johnson  Novavax  I Don't Know	
/ (MM/YYYY)  I Don't Know	 First Dose  Second Dose  Booster(s)  I Don't Know	 Pfizer  Moderna  Johnson & Johnson  Novavax  I Don't Know	
/ (MM/YYYY)  I Don't Know	 First Dose  Second Dose  Booster(s)  I Don't Know	 Pfizer  Moderna  Johnson & Johnson  Novavax  I Don't Know	
/ (MM/YYYY)  I Don't Know	 First Dose  Second Dose  Booster(s)  I Don't Know	 Pfizer  Moderna  Johnson & Johnson  Novavax  I Don't Know	
/ (MM/YYYY)  I Don't Know	 First Dose  Second Dose  Booster(s)  I Don't Know	 Pfizer  Moderna  Johnson & Johnson  Novavax  I Don't Know	
If you have not received any COVID-19 booster vaccinations, would you be willing to be contacted to discuss the benefits and risks of obtaining one?		 Yes  No  I Don't Know	
Would you be willing to receive a yearly COVID-19 vaccination if recommended by your physician?		 Yes  No  I Don't Know	
COVID-19 Infections			
List all COVID-19 infections since you completed the Baseline questionnaire.			
Have you been diagnosed with COVID-19 since your last visit?		 Yes  No  I Don't Know	
When was your COVID-19 Infection Confirmed?	/ (MM/YYYY)  I Don't Know	How was your COVID-19 Infection Confirmed?	 Home Test Kit  Diagnosis by a Healthcare Professional  I Don't Know
Did This COVID-19 Infection Cause You to be Hospitalized?	 Yes  No  I Don't Know	If Yes, About How Many Days Were You in the Hospital?	_____  I Don't Know

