#### 4.3 Patient-Generated Health Data

Subjects will be asked to complete questions specific to their health as outlined below. All questions will be administered electronically through the study application. These measures will be obtained to establish health status and COVID-19 infection(s) acquired after study entry. These measures will be included at baseline and at specified timepoints, as outlined in the [Schedule of Activities](#).

The following patient-generated health data (PGHD) will be collected directly from the participating patient and are specified in [Appendix A](#):

- Study eligibility questions
- Contact information and socio-demographics
- Multiple myeloma diagnosis and disease status
- SARS-CoV-2 vaccination history
- Documented COVID-19 infections and treatments
- COVID-19 specific questions

Participants may request additional information about COVID-19 booster vaccinations. Sponsor will receive notification that a participant has requested additional information. Sponsor will also monitor participant requests.

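### The COVID-19 forms ask for all infections but print one infection block each, so a second infection in the same reporting window has no field

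*Combined protocol and SAP*

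**What the plan says.** Section 4.3 points to Appendix A as the specification of the patient-generated data and gives their purpose: "These measures will be obtained to establish health status and COVID-19 infection(s) acquired after study entry". The wording allows for more than one infection per participant.

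In Appendix A, the baseline form instructs: "List all current and prior COVID-19 infections". The form shared by Time 1 and Time 2 instructs: "List all COVID-19 infections since you completed the Baseline questionnaire". Under each instruction there is one set of fields: month and year of confirmation, method of confirmation, whether the infection led to hospitalization, and length of stay.

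The question that opens the follow-up infection section uses a different starting point from its instruction: "Have you been diagnosed with COVID-19 since your last visit".

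The vaccination part of the follow-up form has a similar instruction, "List all COVID-19 vaccinations received since you completed the Baseline questionnaire", but prints five rows. The baseline vaccination table also has five.

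Section 2.2 lists among the secondary endpoints the percentage of patients reporting a confirmed infection, patient-reported adverse outcomes of confirmed infection, and COVID-19 hospitalization or death taken from EHR data. Section 5 makes the proportion answering the PRO instruments the primary endpoint.

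**The concern.** The instruction and the layout disagree. A participant asked for every infection is given room for one, and where there are two in the window the participant decides which to enter. The vaccination tables on the same forms show that repeated entries were laid out where they were wanted.

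This matters mainly for the patient-reported adverse-outcome endpoint. The only outcome-of-infection fields printed in Appendix A are the hospitalization question, "Did This COVID-19 Infection Cause You to be Hospitalized", and the number of days, and both sit inside the single block. If an infection is not listed, its outcome is not listed either. Counts of patient-reported episodes would then be too low, and the admissions that participants themselves report could be too low as well.

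**Working it through.** The plan states no figure to reproduce. The check is a count of printed entries, set against the visit schedule and the endpoint definitions.

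**1. Entries per form (Appendix A)**

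| Form | Vaccination rows | Infection blocks |
|---|---|---|
| Baseline | 5 | 1 |
| Follow-up, used at Time 1 and Time 2 | 5 each time | 1 each time |

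**2. Entries per participant.** One baseline form and two follow-up forms give 1 + 2 = 3 infection entries: one for the whole history before enrollment and two after it. Two post-enrollment infections can both be entered if one falls before the Time 1 form and the other after it. No field exists for a second pre-enrollment infection, or for a second infection between consecutive questionnaires.

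**3. Length of the windows (Section 4.5).** Time 1 is at Day 30 to 45 and Time 2 at Day 180 to 210. The second window therefore runs from 180 − 45 = 135 days to 210 − 30 = 180 days. If Time 1 is missed, one block has to cover up to 210 days.

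**4. Recall period at Day 180.** A participant who follows the instruction goes back to baseline; one who follows the question goes back to the last visit. Someone infected before Day 30 and again before Day 180 may re-enter the first infection at Day 180, which leaves no room for the second. The confirmation month would often show that the entry is a repeat, but the displaced infection would still be missing. The vaccination section has the same mismatch, with five rows to absorb it.

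**5. Endpoints reached**

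- Primary (PRO response): does not use these fields.
- Percentage of patients reporting a confirmed infection: counted per patient, so a second infection in the same patient adds nothing. The exception is a participant who uses the one block for an episode whose confirmation is unknown and leaves out a test-confirmed one.
- Hospitalization or death: taken from EHR data by two routes in Section 5, not from this form.
- Patient-reported adverse outcomes, and any episode count read into the incidence wording of Section 5: exposed.

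**6. Scale, on assumptions only.** The documents give no infection or reinfection rate. Suppose 20–30% of 200 participants are infected during follow-up: 0.20 × 200 = 40 to 0.30 × 200 = 60. Suppose 2–10% of those are infected twice: 0.02 × 40 = 0.8 to 0.10 × 60 = 6. That is roughly 1 to 6 second infections after enrollment. It is a ceiling on the second episodes lost, because those falling in separate windows can be entered. The result moves in proportion to both assumed rates and is not an estimate from the plan.

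**The case against.** Appendix A is a list of data elements for an electronic application, and the documents do not say whether the infection block repeats on screen. The hospitalization question refers to one particular infection, which fits a block that is shown once per infection. This stands as an ambiguity, so an absolute limit is not shown. It does not remove the mismatch, because Section 4.3 makes Appendix A the specification and the five printed vaccination rows point the other way.

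Three stronger readings are tempting, and the documents do not support them.

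- A reader might infer that no second infection, and no admission it caused, can be recorded at all. The follow-up form is given twice, so infections in different windows each have an entry, and the EHR may still show the admission.
- A reader might infer that a large share of COVID-19 hospitalizations would be lost from the results. That endpoint is ascertained from EHR data. Section 5 restricts it to the institution giving the myeloma care, so an admission elsewhere for an unlisted infection could escape both the EHR and the form, but that restriction is a separate matter.
- A reader might infer that an infection already present at entry would be counted as acquired later. That needs a positive answer about the period since the last visit and a month that is ambiguous or falls after entry. It is speculative, and the single block does not cause it.

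**Conclusion.** The point holds in a limited form. On the forms as printed, the request for all infections cannot be met when two fall in one reporting window, and the participant's account of an admission caused by the unlisted one goes with it. The two recall periods on the follow-up form make this somewhat more likely at Day 180.

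The effect is small and confined to patient-reported episode counts and adverse outcomes. Its size cannot be computed from the documents. The conclusion assumes that the application shows the block as Appendix A prints it. If the block already repeats, what remains is a gap in the specification and the conflict in recall periods. This is a low-priority improvement.

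**What to change.** Make the infection block repeat on the baseline and follow-up forms, with date, method of confirmation, hospitalization and days in hospital recorded for each infection. Printing several rows, as for vaccinations, would also serve. If the application already repeats the block, one line in Appendix A saying so is enough for this part.

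On the follow-up form, use the same recall period in the instruction and the question, for infections and for vaccinations alike.

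The cost is a minor reconfiguration of the form, a revised Appendix A, and a few extra seconds for participants with more than one infection. Other participants see no added burden.

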### 2.2 Study Endpoints

- **Primary endpoint:** Feasibility of obtaining baseline, 30-day, and 6-month clinical and PRO data capture from 200 consented patients.
- **Secondary endpoints:**
  - Percent of patients who enroll on the study platform who had previously received a SARS-CoV-2 booster.

- Percent of patients who enroll on the study platform who went on to receive a SARS-CoV-2 booster after enrollment.
- Percent of patients providing patient reported outcomes (PROs) at each timepoint.
- Among patients providing PROs, percentage for which PROs were viewed by site personnel.
- Percent of patients reporting COVID-19 infection confirmed by home-based or other testing.
- Patient-reported adverse outcomes related to confirmed COVID-19 infection (*as applicable*).
- Hospitalization or death related to COVID-19 as ascertained by full EHR data transmission provided by permission from the patient (*as applicable*).

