## **5 Statistical Considerations**

The accrual goal for this study is the enrollment of 200 participants, defined as eligible subjects who access the portal and consent to participate. The primary end point of this study is the proportion of consented participants who provide responses for the PRO instruments; we will separately track the proportion of consented participants who permission access to clinical data through the EHR. We will estimate the proportions and present them descriptively, with a point estimate and an exact binomial confidence interval at each of the PRO time points (Baseline, Day 30, and Day 180). We will also present descriptively the proportion of consented participants who permission EHR access.

We will also report descriptive statistics for each of the secondary objectives, including the proportion of participants who had received a SARS-CoV-2 booster prior to enrollment; the proportion who received a SARS-CoV-2 booster after enrollment; the incidence of patient-reported COVID-19 infection confirmed

by home-based or other testing (per patient report); and the incidence of patient-reported adverse outcomes related to confirmed COVID-19 infection, including long COVID.

Lastly, we will report descriptive statistics on the incidence of hospitalization (at the primary institution at which the patient received myeloma care) or death related to COVID-19 during the 6-month period of observation. We will report estimates for these metrics from two forms of ascertainment: patient-permissioned EHR data transmission and site-provided EHR data abstraction (received under the Data Hub's overarching umbrella protocol). We may perform exploratory analyses of clinical and laboratory correlates of severe adverse COVID-19 related outcomes, sample size permitting, based on site-provided EHR data abstraction (under the Data Hub's umbrella protocol).

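### Appendix A follow-up forms do not ask about a later admission for an infection current at baseline, and at Time 2 their two look-back periods conflict for infections already reported at Time 1

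*Combined protocol and SAP*

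**What the plan says.** **Baseline form** (Appendix A, After Informed Consent). The infection section carries the instruction "List all current and prior COVID-19 infections". For a listed infection it asks the month and year of confirmation, how it was confirmed, whether it led to hospitalization, and for how many days.

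**Time 1 and Time 2 forms** (Appendix A). The instruction is "List all COVID-19 infections since you completed the Baseline questionnaire". The question directly beneath it is "Have you been diagnosed with COVID-19 since your last visit". The outcome item is again tied to the listed infection: "Did This COVID-19 Infection Cause You to be Hospitalized". No admission date is collected, and no printed item asks about an admission separately from a listed infection.

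**Use of the data.** Section 2.2 has a secondary endpoint based on patient report, "Patient-reported adverse outcomes related to confirmed COVID-19 infection", which Section 5 will summarize as an incidence. A separate endpoint is "Hospitalization or death related to COVID-19 as ascertained by full EHR data transmission provided by permission from the patient". For that one Section 5 states: "We will report estimates for these metrics from two forms of ascertainment: patient-permissioned EHR data transmission and site-provided EHR data abstraction". Section 5 also limits hospitalization to the institution where the patient receives myeloma care. The Study Summary's secondary objective names both patient report and EHR data as means of monitoring infections that lead to hospitalization. Section 4.3 describes the purpose of the patient-entered questions as to "establish health status and COVID-19 infection(s) acquired after study entry".

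**The concern.** Admission comes after diagnosis, often by some days. An answer given when an infection is first reported can therefore be out of date soon afterwards, and a form that asks once per infection needs a way to update it.

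Two situations test this. A participant may be positive at Day 0, report no hospitalization at baseline, and be admitted on Day 5. Another may be diagnosed on Day 28, complete Time 1 on Day 30, and be admitted on Day 35.

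At stake is the completeness of patient-reported admissions, since hospitalization is the only COVID-19 outcome item printed in Appendix A. Patient report is also the natural source for admissions to other hospitals, which the Section 5 EHR measure leaves out.

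**Working it through.** The plan gives no figure to reproduce. The check sets the two follow-up lines against three cases, then sizes the gap under stated assumptions.

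**Step 1. Visit timing** (Section 4.5). Time 1 falls on Day 30 to 45 and Time 2 on Day 180 to 210. At Time 2 the instruction looks back to baseline and the diagnosis question looks back to Time 1, so they differ by 30 to 45 days. The interval from Time 1 to Time 2 is 180 − 45 = 135 to 210 − 30 = 180 days.

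**Step 2. Cases**

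| Case | Covered by the instruction (since baseline)? | Covered by the question (since last visit)? | Result |
|---|---|---|---|
| A. Infection current at baseline, admission after the baseline form | No | No | Admission not elicited |
| B. Infection reported at Time 1, admission before Time 2 | Yes | No | Depends on which line is followed |
| C. Infection new since the last form, admission before the next form | Yes | Yes | Captured |

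Case A does not depend on any skip logic, because the infection lies outside both periods. In case B, a participant who follows the question does not list the infection again and the admission is lost. One who follows the instruction lists it again and reports the admission, but the infection now appears on two forms with only month and year to match them. A duplicate would not change the percentage of patients who report any infection. It would inflate a count of infections, or a denominator of infections.

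**Step 3. Size.** Assume a steady rate of infections that lead to admission, and a mean delay of d days from diagnosis to admission. Admissions over 180 days are then proportional to 180. Those whose diagnosis and admission fall on either side of one given form are proportional to d. The share missed is d/180 at baseline, and a further d/180 at Time 1 if participants follow the diagnosis question at Time 2.

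| d (assumed) | Baseline gap, d/180 | Both, 2d/180 |
|---|---|---|
| 3 days | 1.7% | 3.3% |
| 7 days | 3.9% | 7.8% |
| 10 days | 5.6% | 11.1% |

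**Step 4. In admissions.** The documents give no expected number. With 4 admissions (2% of 200, assumed), the baseline gap is 4 × 1.7% to 4 × 5.6%, or 0.07 to 0.22 of an admission; both together are 0.13 to 0.44. With 10 admissions (5% of 200, assumed), the figures are 0.17 to 0.56 and 0.33 to 1.1.

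**The case against.** The strongest reply is that the hospitalization endpoint does not use this item. Sections 2.2 and 5 estimate it from two EHR sources, the primary endpoint is PRO response, and every analysis is descriptive. That stands. A reader might infer that the forms bias the hospitalization estimate or create false disagreement with the EHR. The documents do not support this: patient report does not feed that estimate, and the plan proposes no comparison of patient report with EHR data.

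A reader might also infer that an admission following an infection reported at Time 1 is never captured. That goes too far. The instruction at Time 2 covers the infection, so a participant who follows it will report the admission. Whether a negative answer to the diagnosis question hides the hospitalization item is not printed.

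A third tempting reading is that a second infection has no field, because one infection record is printed against five vaccination rows. Appendix A lists data elements rather than form behavior, and its instruction to list all infections suggests a repeatable entry. Section 4.3 also refers to COVID-19 treatment data and specific questions for which no corresponding treatment item is printed, so the appendix may not show the whole instrument. This is a matter to confirm, not a finding.

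Finally, Section 4.3 speaks of infections acquired after entry, which arguably puts case A out of scope. This has some force. However, the adverse-outcome endpoint in Section 2.2 carries no such limit, and the baseline form collects current infections. The steady-rate model probably overstates case A as well, because people who are acutely ill may delay enrolling.

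**Conclusion.** The point holds in a limited form. As printed, the follow-up forms do not elicit an admission after baseline for an infection current at baseline. At Time 2 they give conflicting look-backs for an infection already reported at Time 1, with either a missed admission or a duplicate infection as the possible result.

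What is affected is the patient-reported adverse-outcome endpoint and the patient-report part of the Study Summary objective. Patient report is also the natural way to learn of admissions outside the main myeloma institution.

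The shares in the working rest on an assumed steady infection rate and assumed delays of 3 to 10 days. At the assumed counts of 4 to 10 admissions, the expected loss is below one admission except at the top of the range. This is a cheap improvement to data capture and does not threaten the study's main conclusions.

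**What to change.** 1. Use one look-back period for the instruction and the diagnosis question on the Time 1 and Time 2 forms. Counting from the last completed form avoids listing an infection twice and still works for someone who skips Time 1.
2. Add one item to both forms, shown whatever the answer on new diagnoses. For example: *Since you last completed a study form, have you been admitted to hospital because of COVID-19, including for an infection you have already told us about?* Collect the admission date and the number of days.
3. Confirm that the infection block can be repeated in the application, and say so in Appendix A.

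The cost is one extra question, a few seconds of participant time, and a minor amendment to an electronic form. Aligning the look-back alone would not close the baseline gap; the added item does that.
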